## 1.2. Study Design

This is a randomized, double-blind placebo-controlled, parallel, multicenter, interventional study in participants with moderate-to-severe plaque psoriasis. This Phase 2a study is focused on proof of-concept and will assess the efficacy, safety, and tolerability of JNJ-77242113 (an IL-23R peptide antagonist) orally administered as a delayed release tablet formulated with an CCI [REDACTED]

[REDACTED] This study will be conducted in parallel with the complementary study 77242113PSO2001, a Phase 2b randomized, double-blinded, dose-ranging, placebo-controlled study designed to evaluate the efficacy and safety of JNJ-77242113, formulated as an immediate-release oral tablet CCI [REDACTED] in adults with moderate-to-severe plaque psoriasis. The target population for this study intervention consists of participants 18 to 75 years of age (or the legal age of consent if it is higher in the jurisdiction in which the study is taking place), with moderate to severe psoriasis of at least 26 weeks duration, primarily defined as a total BSA  $\geq 10\%$ , total PASI  $\geq 12$ , and total Investigator Global Assessment (IGA)  $\geq 3$  at screening and baseline.

A target of 80 participants will be enrolled in this study. Participants will be randomized to receive 1 of the 2 JNJ-77242113 doses of an oral delayed release tablet CCI [REDACTED] or placebo in a 3:3:2 ratio (30:30:20) using dynamic central randomization, stratified by baseline weight ( $\leq 90$  kg,  $>90$  kg).

The treatment arms for this study will be as follows:

**Group 1:** 10 mg JNJ-77242113 oral delayed release tablet CCI [REDACTED] administered once daily from Week 0 through Week 16.

**Group 2:** 50 mg JNJ-77242113 oral delayed release tablet CCI [REDACTED] administered once daily from Week 0 through Week 16.

**Group 3:** Placebo oral delayed release tablet, administered once daily from Week 0 through Week 16.

[figure not shown]

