## 3. SAMPLE SIZE DETERMINATION

This study is designed to assess the clinical response, safety/tolerability, and pharmacology of JNJ-77242113 CCI in participants with moderate-to-severe plaque psoriasis. The sample size is evaluated based on the primary endpoint of a PASI 75 response at Week 16. The sample size of 80 participants was chosen in order to have sufficient power to detect a difference between the JNJ-77242113 CCI (30 participants for each of low and high dose groups) and the placebo group (20 participants).

The assumptions for the sample size and power calculations were mainly based on the clinical data from guselkumab Phase 3 clinical studies that evaluated the safety and efficacy in the treatment of adult participants with moderate-to-severe plaque psoriasis.

The null hypothesis is to be tested at an overall Type 1 error rate of 0.10 (2-sided). Assuming PASI75 response rates at Week 16 are 5% to 10% for placebo and 40% to 80% for JNJ-77242113 CCI, a sample size of 20 participants in the placebo group and 30 participants in the JNJ-77242113 CCI will provide at least 90% power to detect a 35% difference between the JNJ-77242113 CCI and placebo groups in the proportion of participants achieving a PASI 75 response at Week 16 based on a 2-sample Z-test.

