#### 5.3.3.3.1. Supplementary Analysis 1 (Hypothetical Estimand)

Under this estimand, PASI 75 response will be considered missing after an intercurrent event and missing data will be imputed using multiple imputations (MI) by fully conditional specification (FCS).

More specifically, the missing PASI75 responses will be imputed with FCS logistic regression including treatment group, baseline PASI score, and PASI75 response status through Week 16 in the model with seed = 789 and 500 imputations. The proportion difference of PASI75 response between each JNJ-77242113 group and placebo group at Week 16 adjusted for baseline weight category ( $\leq 90$  kg,  $> 90$  kg) using Mantel-Haenszel weight and its 90% CI combining multiple datasets will also be provided. A CMH test stratified by baseline weight category ( $\leq 90$  kg,  $> 90$  kg) will be used to obtain the CMH statistic for each imputed dataset.

The values of the general association test statistics from the CMH test for each imputed dataset will be transformed using the Wilson-Hilferty transformation to create a more normal distributed statistic:

$$Z = \frac{(CMH)^{(1/3)} - 7/9}{(2/9)^{(1/2)}}.$$

The resulting transformed values will be combined using SAS PROC MIANALYZE and obtain the overall p-value for the CMH test. Difference in PASI75 response rates at Week 16 between each of the active intervention groups and the placebo group at Week 16 adjusted for baseline weight category using Mantel-Haenszel weight and its 90% CI combining multiple datasets will also be provided.

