##### 5.4.2.1.1. Analysis for Supplementary Estimands

The analyses specified in Section 5.3.2.2.1 (Hypothetical Estimand) and Section 5.3.2.2.2 (Treatment Policy Estimand) for supplementary estimands will be applied to the following secondary endpoints:

- Proportion of participants achieving PASI 90 ( $\geq 90\%$  improvement from baseline in PASI) at Week 16
- Proportion of participants achieving PASI 100 (100% improvement from baseline in PASI) at Week 16
- Proportion of participants achieving an IGA score of cleared (0) or minimal (1) at Week 16
- Proportion of participants achieving an IGA score of cleared (0) at Week 16

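### The supplementary multiple imputation of binary response has no rule for sparse placebo data and omits the weight stratifier, so it is at material risk of inflating the placebo response rate

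*SAP*

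**What the plan says.** The imputation model is set out once, in SAP 5.3.3.3.1. Response after any of the three intercurrent events is set to missing, and missing PASI 75 status is "imputed with FCS logistic regression including treatment group, baseline PASI score, and PASI75 response status through Week 16 in the model", with 500 imputations. No penalty, augmentation, iteration limit or fallback for sparse visits is given.

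Each imputed dataset is analysed by a CMH test and a Mantel-Haenszel difference, both stratified by baseline weight. Each CMH statistic is put through a Wilson-Hilferty transformation, and then: "The resulting transformed values will be combined using SAS PROC MIANALYZE and obtain the overall p-value for the CMH test". The tail of that p-value is not stated.

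The same imputation serves the treatment policy estimand (SAP 5.3.3.3.2). SAP 5.4.1.3 carries both supplementary estimands to PASI 90, PASI 100, IGA 0/1 and IGA 0. SAP 5.4.2.1.1 confirms that the analyses "for supplementary estimands will be applied to the following secondary endpoints". No separate model is written for those four endpoints.

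The design inputs are in SAP 3 and 1.2. Allocation is to "placebo in a 3:3:2 ratio (30:30:20) using dynamic central randomization", stratified by weight at 90 kg. The rates are "Assuming PASI75 response rates at Week 16 are 5% to 10% for placebo and 40% to 80% for JNJ-77242113".

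**The concern.** Logistic regression has no finite maximum-likelihood estimate when one level of a covariate contains no events. Treatment group is such a covariate, and the placebo level holds 20 people of whom only 1 or 2 are expected to respond. If none does, the placebo coefficient runs off towards minus infinity and its estimated variance grows faster still. The random parameter draws that multiple imputation needs then give placebo response probabilities close to 0 or close to 1, almost at random. FCS also models each earlier PASI visit (Weeks 1, 2, 4, 8 and 12 in Protocol 1.3), where responders should be rarer.

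Separately, an imputation model should contain the variables used in the analysis. Baseline weight category stratifies the randomisation, the CMH test and the Mantel-Haenszel difference, but it is absent from the imputation model.

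At stake is the value of the robustness check. Protocol 9.4.2 (Primary Endpoint Analysis) promises analyses under different missing-data approaches. These are the only multiple-imputation analyses of the primary endpoint and of four binary secondary endpoints. If they add placebo responders artificially, they could make a sound primary result look fragile.

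**Working it through.** **The plan's own figure.** The SAP gives no figure for the imputation; its only computed figure is power of at least 90% for a 35-point difference. With 20 placebo, 30 active, two-sided alpha 0.10 and unpooled variance:

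- 5% v 40%: SE = √(0.05×0.95/20 + 0.40×0.60/30) = 0.1019; 0.35/0.1019 − 1.645 = 1.79; power 96.3%.
- 10% v 45%: SE = √(0.10×0.90/20 + 0.45×0.55/30) = 0.1129; 0.35/0.1129 − 1.645 = 1.45; power 92.7%.

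Exact enumeration gives 94.8% and 90.2%, so the figure reproduces. A pooled-variance formula gives 91.8% and 87.6%.

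**How often no placebo participant responds.** Expected responders are 20×0.05 = 1 to 20×0.10 = 2. The probability of none among 20 is:

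- 0.95^20 = 36% and 0.90^20 = 12% for PASI 75 at Week 16;
- 0.98^20 = 67% and 0.99^20 = 82% at placebo rates of 2% and 1% (assumed for the stricter endpoints);
- 82% and 67% at an early visit whose rate is one fifth of the 5% or 10% Week 16 rate (assumed).

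**What the fit does then.** With 0 of 20 responders, each Newton step lowers the placebo log-odds b by about 1, and SE ≈ exp(−b/2)/√20. When SE is large, the mean imputed probability over draws from N(b, SE²) is close to Φ(b/SE).

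- 8 iterations: b = −9.2, SE = 22.3, mean 0.34.
- 12 iterations: b = −13.2, SE = 164.6, mean 0.47.
- 25 iterations: mean 0.50.

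With 17 observed and a baseline covariate added, 0 responders gives 0.35 to 0.50, depending on when the fit stops. In the arm-only fit, 1 or 2 responders of 20 give 0.07 and 0.12.

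**Full-visit simulation.** This used arms of 30/30/20, PASI 75 at all six post-baseline visits and unaugmented FCS logistic imputation. Dropout, response time-course and within-person correlation are assumptions.

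| Placebo rate | Dropout | Mean imputed placebo response | True rate among missing | Placebo rate after imputation v true |
|---|---|---|---|---|
| 5% | 10% | 0.32 | 0.01 | 9.3% v 6.0% (+3.3) |
| 5% | 20% | 0.39 | 0.05 | 12.3% v 5.3% (+7.0) |
| 10% | 10% | 0.36 | 0.04 | 13.6% v 10.8% (+2.8) |
| 10% | 20% | 0.41 | 0.09 | 16.6% v 10.5% (+6.1) |

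Imputed placebo response was 0.43 to 0.57 when no placebo responder was observed, and still 0.27 to 0.39 when at least one was. The low-dose rate hardly moved. At 20% dropout the low-dose difference fell from 39.0 − 5.3 = 33.7 to 39.0 − 12.3 = 26.7 points in the 5% scenario, and from 43.7 − 10.5 = 33.2 to 43.2 − 16.6 = 26.6 in the 10% scenario. With data augmentation at 20% dropout, mean imputed placebo response was 0.15 and 0.20, and the shift in the placebo rate was 2.7 and 2.6 points.

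**Pooled p-value.** For k degrees of freedom the Wilson-Hilferty constants are 1 − 2/(9k) and √(2/(9k)). At k = 1 these are 7/9 and √(2/9), as the SAP has them. At CMH = 2.706, Z = (1.393 − 0.778)/0.471 = 1.306. The upper tail is 0.096 (chi-square p = 0.100), and the two-sided value is 0.192. At CMH = 3.841 the upper tail is 0.047 (chi-square p = 0.050).

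**The case against.** The strongest reply is that this is one model over about 80 people, that zero Week 16 placebo responders is the minority case, and that nothing in the SAP forbids an augmented likelihood, which would remove most of the problem. The primary analysis (SAP 5.3.3.1) treats missing data as non-response and does not use this imputation. Completer and per-protocol analyses (SAP 5.3.3.2 and 5.3.3.4) also test the primary result. The bias works against the drug, and 3 to 7 points is modest beside a planned difference of 35.

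Most of this stands and sets the limits of the point. It does not remove it: the augmentation is not specified, the result depends on an unstated stopping rule, and the simulated inflation persists when one or more placebo responders are seen. Omission of weight is also a fair criticism, although no numerical consequence has been shown and stratified randomisation limits imbalance between arms.

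A reader might infer four stronger things that the documents do not support:

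- **The model is fitted within the placebo arm and must separate.** Treatment is a covariate in a pooled model, and separation at Week 16 has a 12% to 36% chance on the SAP's rates.
- **Placebo response is always imputed near 0.5.** That applies when no placebo responder is observed; the overall simulated average was 0.32 to 0.41.
- **The pooling step is wrong.** The formula is correct for 1 df; only the tail is unstated.
- **The same binary model is spelled out for PASI 90, PASI 100 and IGA.** It reaches them by cross-reference: SAP 5.4.1.3 cites the detailed section, while SAP 5.4.2.1.1 cites the estimand definition, which only calls for imputation under missing at random.

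**Conclusion.** The concern holds as a weakness of the supplementary imputation analyses. It does not call the primary result into question. Sparse placebo response is foreseeable from the SAP's own assumptions and the plan has no provision for it. Better information, the PASI score itself, is already collected at every visit.

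The 12% and 36% probabilities follow directly from the SAP. The 3-to-7-point inflation does not: it rests on assumed dropout, time-course and correlation, on an unaugmented fit, and on only 26 to 60 simulated trials per scenario, so it should be read as approximate. The direction is towards a smaller treatment effect, so the risk is a misleading signal of fragility rather than a false claim of efficacy. The p-value tail is a clarification only.

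**What to change.** In SAP 5.3.3.3.1, and by reference in 5.3.3.3.2, 5.4.1.3 and 5.4.2.1.1:

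1. Impute the PASI total score at each visit by FCS predictive mean matching, with treatment group, baseline PASI, baseline weight category and PASI at the other visits. Derive PASI 75, 90 and 100 in each completed dataset. If regression imputation is preferred, bound the values and specify truncation and rounding, because PASI 100 needs a score of exactly 0 and an unrounded continuous draw will not give one.
2. Impute IGA by ordinal logistic regression with an augmented likelihood, also including weight category, and derive IGA 0/1 and IGA 0.
3. State that the overall p-value is the upper-tail probability of the pooled Wilson-Hilferty statistic.

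The cost is SAP wording and a changed imputation program, with no new data. The downside is a modelling assumption for PASI scores. If the binary model is kept, adding an augmented likelihood and weight category is the minimum; in the simulations at 20% dropout, augmentation alone cut the shift in the placebo rate to just under 3 points.

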#### 5.3.3.3.2. Supplementary Analysis 2 (Treatment Policy Estimand)

The primary endpoint will also be analyzed utilizing the treatment policy estimand. For participants who experience an intercurrent event through Week 16, the analysis will be performed using observed data regardless of intercurrent events. Missing data will be imputed using multiple imputation method specified in Section 5.3.2.2.1.

#### 5.3.3.4. Per Protocol Analysis

The primary efficacy endpoint will be evaluated in the PP population based on the primary estimand except that ICE 3 will not be applied. Participants with ICE 3 who do not complete all scheduled study administration prior to Week 16 will be excluded from the per protocol analysis. The same data handling rule and analysis method specified in Section 5.3.3.1 will be applied.

## 5.4. Secondary Endpoints Analysis

No multiplicity adjustment will be made for the secondary endpoints. All statistical testing will be performed at the 2-sided 0.1 significance level. Nominal p-values will be presented.

### 5.4.1. Secondary Endpoint(s)

**The secondary objective is to** characterize additional efficacy of JNJ-77242113 versus placebo in participants with moderate-to-severe plaque psoriasis.

The secondary endpoints to address these objectives are the following:

1. Proportion of participants achieving PASI 90 ( $\geq 90\%$  improvement from baseline in PASI) at Week 16
2. Proportion of participants achieving PASI 100 (100% improvement from baseline in PASI) at Week 16
3. Proportion of participants achieving an IGA score of cleared (0) or minimal (1) at Week 16
4. Proportion of participants achieving an IGA score of cleared (0) at Week 16
5. Change from baseline in PASI total score at Week 16
6. Change from baseline in BSA at Week 16

#### 5.4.1.1. Definition of Endpoint(s)

##### 5.4.1.1.1. Psoriasis Area and Severity Index (PASI)

Refer to section [5.3.1](#) for details.

##### 5.4.1.1.2. Investigator's Global Assessment (IGA)

The IGA documents the investigator's assessment of the participant's psoriasis at a given time point. Overall lesions are graded for induration, erythema, and scaling. The participant's psoriasis is assessed as cleared (0), minimal (1), mild (2), moderate (3), or severe (4).

##### 5.4.1.1.3. Body Surface Area (BSA)

Body Surface Area is a commonly used measure of severity of skin disease. It is defined as the percentage of surface area of the body involved with the condition being assessed, (ie, plaque psoriasis). The handprint method for assessing BSA will be used in this study, where the surface area of the patient's hand including the palm and all five digits is used as a guide to estimate 1% BSA ([Long 1992](#); [Rossiter 1996](#); [Thomas 2007](#)).

### 5.4.1.2. Main Estimands for Secondary Endpoints

The secondary endpoints will be analyzed using the primary estimand described in section 5.3.2.1. as the main estimand. This main estimand will be considered for both binary and continuous

secondary endpoints. The analysis strategy for ICEs and missing data will be handled in the same manner as the primary estimand for the primary endpoint.

- ICEs 1-2: Composite strategy
- ICE 3: Treatment policy strategy

The study intervention and population are the same as the primary estimand.

## **BINARY ENDPOINTS**

**Variables:** Binary response variable (eg, PASI 90 responses at Week 16). A participant with an intercurrent event in categories 1-2 defined below will be considered as a non-responder.

**Population-level summary:** Difference in the proportions of participants achieving a clinical response between the treatment groups.

The variables and population -level summaries for the other secondary binary endpoints are similarly described.

## **CONTINUOUS ENDPOINTS**

**Variable (Endpoint):** change from baseline to Week 16 (change = Week 16 - baseline).

- Participants who have intercurrent events in categories 1, 2 through Week 16 will be assigned a zero change from baseline from the point of the ICE, regardless of the observed data.

**Population-level summary:** LSMean difference in change from baseline in eg, PASI score at Week 16 between JNJ-77242113 treatment groups and the placebo group.

The variables and population -level summaries for the other secondary continuous endpoints are similarly described.

### **5.4.1.3. Supplementary Estimands**

The supplementary estimands defined in Section 5.3.3.3.1 (Hypothetical Strategy) and Section 5.3.3.3.2 (Treatment Policy Strategy) for the primary endpoint will also be used for binary secondary endpoints:

- Proportion of participants achieving PASI 90 ( $\geq 90\%$  improvement from baseline in PASI) at Week 16
- Proportion of participants achieving PASI 100 (100% improvement from baseline in PASI) at Week 16
- Proportion of participants achieving an IGA score of cleared (0) or minimal (1) at Week 16

- Proportion of participants achieving an IGA score of cleared (0) at Week 16

The following table provides the list of variables, summary measure (population-level summary) and intercurrent event strategy for secondary endpoints.

| Endpoint | Variable   | Summary Measure (Population-level summary)   | Intercurrent Event Strategy   |
|----------|--|--|---|
| 1        | Binary response variable, where a responder is defined as a participant achieving a PASI 90 response at Week 16                          | Difference in the proportions of participants achieving a PASI 90 response at Week 16 between JNJ-77242113 treatment groups and placebo group.                         | Same analysis strategies as the primary estimand as specified in section 5.3.2.1 and two supplementary estimands specified in section 5.3.2.2   |
| 2        | Binary response variable, where a responder is defined as a participant achieving a PASI 100 response at Week 16                         | Difference in the proportions of participants achieving a PASI 100 response at Week 16 between JNJ-77242113 treatment groups and placebo group.                        | Same analysis strategies as the primary estimand as specified in section 5.3.2.1 and two supplementary estimands specified in section 5.3.2.2   |
| 3        | Binary response variable, where a responder is defined as a participant achieving an IGA scores of cleared (0) or minimal (1) at Week 16 | Difference in the proportions of participants achieving an IGA score of cleared (0) or minimal (1) at Week 16 between JNJ-77242113 treatment groups and placebo group. | Same analysis strategies as the primary estimand as specified in section 5.3.2.1 and two supplementary estimands specified in section 5.3.2.2   |
| 4        | Binary response variable, where a responder is defined as a participant achieving an IGA scores of cleared (0) at Week 16                | Difference in the proportions of participants achieving an IGA score of cleared (0) at Week 16 between JNJ-77242113 treatment groups and placebo group.                | Same analysis strategies as the primary estimand as specified in section 5.3.2.1 and two supplementary estimands specified in section 5.3.2.2   |
| 5        | Continuous variable, change from baseline in PASI score at Week 16 (change = Week 16 - baseline)   | LSMean difference in change from baseline in PASI at Week 16 between JNJ-77242113 treatment groups and the placebo group.  | Same analysis strategies as the primary estimand specified in section 5.4.1.2. Participants who have intercurrent events in categories 1, 2 through Week 16 will be assigned a zero change from baseline from the |

|   |   |   |  |
|---|---|---|--|
|   |   |   | point of the ICE, regardless of the observed data.   |
| 6 | Continuous variable, change from baseline in BSA at Week 16 (change = Week 16 - baseline) | LSMean difference in change from baseline at Week 16 between JNJ-77242113 treatment groups and placebo group. | Same analysis strategies as the primary estimand specified in section 5.4.1.2. Participants who have intercurrent events in categories 1, 2 through Week 16 will be assigned a zero change from baseline from the point of the ICE, regardless of the observed data. |

#### 5.4.2. Analysis Methods

The secondary efficacy analysis of data will be based on the FAS. The endpoints will be summarized by intervention group. Simple descriptive statistics, such as n, mean, SD, median, IQ range, minimum and maximum for continuous variables and counts and percentages for discrete variables will be used to summarize most data. All statistical testing will be performed at the 2-sided 0.1 significance level. Nominal p-values will be presented. No adjustments for multiple comparisons will be made for the secondary endpoints.

##### 5.4.2.1. Binary Endpoints

The binary secondary endpoints at Week 16 will be analyzed using the estimand described in section 5.4.1.2. The analysis strategy for ICEs and missing data will be handled in the same manner as the primary estimand for the primary analysis. The proportions of participants achieving the above secondary efficacy endpoints will be summarized for each intervention group.

The Cochran-Mantel-Haenszel chi-square statistic stratified by baseline weight category ( $\leq 90$  kg,  $> 90$  kg) at a 2-sided significance level of 0.1 will be used. Difference in response rates between each of the active and placebo groups at Week 16 adjusted for baseline weight category ( $\leq 90$  kg,  $> 90$  kg) using Mantel-Haenszel weight and the corresponding 90% CI will be presented.

The Fisher's Exact test will be used for treatment comparisons in binary response endpoints. The proportion differences between JNJ-77242113 groups and placebo and the exact confidence intervals will be provided.

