### 9.4.3. Secondary Endpoint(s)

In addition to the primary endpoint analysis, the analyses for secondary efficacy endpoints will be performed. Additional efficacy analyses may be performed and will be documented in the SAP.

- The proportion of participants who achieve a PASI 100 response at Week 16, will be compared between each of the JNJ-77242113 **CCI** and the placebo group.
- The proportion of participants who achieve a PASI 90 response at Week 16, will be compared between each of the JNJ-77242113 **CCI** and the placebo group.

- The change from baseline in PASI total score at Week 16 will be compared between each of the JNJ-77242113 CCI and the placebo.
- The proportion of participants who achieve an IGA score of cleared (0) at Week 16 will be compared between each of the JNJ-77242113 CCI and the placebo group.
- The proportion of participants who achieve an IGA score of cleared (0) or minimal (1) at Week 16 will be compared between each of the JNJ-77242113 CCI and the placebo group.
- The change from baseline in BSA at Week 16 will be compared between each of the JNJ-77242113 CCI and the placebo group.

Categorical data will be analyzed using CMH test, stratified by the baseline weight ( $\leq 90$  kg,  $>90$  kg), to compare each of the JNJ-77242113 with CCI groups compared with placebo. For continuous efficacy endpoints, treatment comparisons will be performed using a Mixed-Effect Model Repeated Measure (MMRM) model. The MMRM model will have treatment group, baseline weight ( $\leq 90$  kg,  $>90$  kg), and baseline value for the corresponding efficacy endpoint as explanatory factors. The Least Square mean ( $LS_{\text{mean}}$ ) estimates, and their corresponding 95% CI will be provided at each time point. In addition, the estimates of  $LS_{\text{mean}}$  difference and 95% CIs between the JNJ-77242113 CCI and placebo groups will be provided.

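### SAP 5.4.2.1 prescribes two tests and two interval methods for the same binary secondary comparisons without saying which is supportive, and the Mantel-Haenszel interval undercovers if it uses the normal approximation

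*SAP*

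**What the plan says.** SAP 5.4.2.1 starts with "The Cochran-Mantel-Haenszel chi-square statistic stratified by baseline weight category", tested at two-sided 0.1, and a difference in response rates adjusted for weight by Mantel-Haenszel weights with a 90% CI. Its next paragraph says that Fisher's "Exact test will be used for treatment comparisons in binary response endpoints", and promises differences with exact confidence intervals. That paragraph gives no strata, no sparse-data trigger, no sensitivity label and no order of precedence. It also gives no level or construction for the exact interval. SAP 5.5.2.1 carries the same methods to the exploratory binary endpoints.

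Elsewhere only one test is named. Protocol 9.4.3 says "Categorical data will be analyzed using CMH test, stratified by the baseline weight". SAP 5.1 names the stratified CMH alone for binary efficacy endpoints, and SAP 5.3.3.1 does so for the primary endpoint. SAP Appendix 2, which lists changes to protocol-planned analyses, reads N/A.

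On level, SAP 5.4.2 says "All statistical testing will be performed at the 2-sided 0.1 significance level". The p-values are nominal and carry no multiplicity adjustment. Protocol 9.4.2.1 specifies a normal approximation for the primary endpoint's Mantel-Haenszel interval; SAP 5.4.2.1 names no approximation for the secondary ones.

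**The concern.** Four endpoints at two doses make 8 comparisons. Under 5.4.2.1 each gets two p-values and two intervals, so 16 of each, all prescribed in equally firm terms. Because these tests are nominal and unadjusted, a fixed method is the main safeguard on how they are reported. One test respects the randomisation stratum and the other ignores it, and in small samples they can fall on opposite sides of 0.10.

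The interval matters separately. PASI 100 and IGA 0 may leave the placebo arm of 20 with no responders or almost none. A normal-approximation interval then becomes too narrow, and can exclude zero when its companion test is not significant.

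**Working it through.** **Inputs from the documents.** Group sizes, SAP 3: "a sample size of 20 participants in the placebo group and 30 participants in the" active groups. Two-sided level 0.10, SAP 5.4.2. PASI 75 rates, SAP 3: "response rates at Week 16 are 5% to 10% for placebo and 40% to 80% for" active. No rates are given for PASI 90, PASI 100, IGA 0/1 or IGA 0.

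**Assumed here.** All low-rate scenarios, the split between weight strata, and the normal approximation for the secondary intervals.

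**1. The plan's own figure.** SAP 3 states at least 90% power for a 35-point difference by a two-sample Z-test. With unpooled variance:
- 5% vs 40%: SE = √(0.05×0.95/20 + 0.40×0.60/30) = 0.1019; 0.35/0.1019 − 1.645 = 1.79; power 96.3%.
- 10% vs 45%: SE = √(0.10×0.90/20 + 0.45×0.55/30) = 0.1129; 0.35/0.1129 − 1.645 = 1.45; power 92.7%.

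The figure reproduces. With pooled variance the two values are 91.8% and 87.6%.

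**2. One table by hand.** In a single stratum, CMH X² = (49/50)·(difference)²/[p̄(1−p̄)(1/20+1/30)]. For 0/20 vs 4/30, p̄ = 0.08, so X² = 0.98×0.01778/0.00613 = 2.84 and p = 0.092. Fisher's p = [C(30,4)+C(20,4)]/C(50,4) = (27,405+4,845)/230,300 = 0.140. Likewise:
- 1/20 vs 7/30: CMH 0.086, Fisher 0.123.
- 2/20 vs 9/30: CMH 0.098, Fisher 0.163.

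**3. All tables.** There are 21×31 = 651 possible outcomes. The tests split at 0.10 in 28 of them, and in all 28 CMH is significant and Fisher is not. Weighting by binomial probabilities:

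| Placebo vs active | Split, one stratum | Split, two weight strata (simulated) |
|---|---|---|
| 5% vs 40% | 3.6% | 2.2–2.8% |
| 10% vs 45% | 4.9% | 3.1–3.8% |
| 5% vs 60% | 0.1% | 0.1% |
| 10% vs 80% | 0.0% | 0.0% |
| 5% vs 25% (assumed) | 11.2% | about 10% (one setting) |
| 2% vs 15% (assumed) | 15.9% | 16% |
| 0% vs 15% (assumed) | 20.3% | not run |

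The simulations used weight splits of 50/50 or 65/35 and stratum odds ratios of 1 or 2. A Fisher-only rejection had probability 0.0% in every setting.

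**4. The normal-approximation interval.** Assume two equal strata, 10+10 placebo and 15+15 active. The Mantel-Haenszel weight is 10×15/25 = 6 in each, so the estimate is the mean of the two stratum differences. Its variance is ¼ of the sum over strata of p̂(1−p̂)/n for both arms. Coverage of the 90% interval by full enumeration:
- 5% vs 40% and 10% vs 45%: about 87%.
- 0% vs 5%, 10%, 15%: 77%, 79%, 82%.
- 1% vs 5%, 10%: 77%, 79%. At 1% vs 15% it recovers to about 86%.

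The interval has zero width when neither arm has a responder. At 0% vs 5% that has probability 0.95³⁰ = 21%; at 0% vs 10%, 0.90³⁰ = 4%; at 0% vs 15%, 0.85³⁰ = 0.8%.

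It can also contradict the CMH test. For 0/20 vs 3/30, unstratified, the lower limit is 0.10 − 1.645×√(0.10×0.90/30) = +0.010, while the CMH p is 0.149.

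The stratified Miettinen-Nurminen interval, in the same enumeration, covers about 90% at design rates and at least 92% in the near-empty cells.

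**The case against.** The documents lean clearly towards CMH. Protocol 9.4.3, SAP 5.1 and SAP 5.3.3.1 name nothing else, no change from the protocol is declared, and within 5.4.2.1 CMH comes first and is the test tied to the 0.1 level. That stands: precedence is implied, though never stated. A reader might infer that the plan leaves the choice wholly open, and the text does not support that.

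A reader might also infer that the second test invites selection that inflates false positives. It does not. Every split has CMH significant and Fisher not, so Fisher's test adds no rejections beyond those of the protocol's own test. These are also nominal secondary p-values in a phase 2a study.

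Nor do the documents support saying that the tests often disagree. At design rates the split is a few percent, and near zero for larger effects. Counting trials with at least one split among the 8 comparisons gives about 15–61% in three assumed efficacy scenarios. That rests on rates and a correlation the plan does not give, so I do not rely on it.

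On the intervals, it is fair to say that the poorest coverage sits in a corner with active rates of 5–15%, and that 5.4.2.1 already offers exact intervals for sparse cells. But those intervals have no stated level or method, and the shortfall to about 87% appears at the design's own rates.

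**Conclusion.** The point holds as a gap in specification and as an interval problem. It is not an error-rate problem. SAP 5.4.2.1 mandates two tests and two interval methods for each comparison and does not say which is supportive. Disagreement at 0.10 is about 2–5% per comparison at the 35-point design difference. It reaches about 11–20% only under assumed low rates, which are plausible for PASI 100 or IGA 0.

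If the secondary Mantel-Haenszel interval uses the normal approximation, it undercovers modestly at design rates and materially when the placebo arm is nearly empty. That reading is carried over from the primary endpoint in the protocol. The exact coverage depends on the weight split, taken here as equal. The primary test is unaffected.

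**What to change.** In SAP 5.4.2.1, state that the weight-stratified CMH is the main test for binary endpoints, as in the protocol, and that Fisher's test and the exact interval are sensitivity results. Give the level and construction of the exact interval. Compute the 90% CI for the weight-adjusted difference by a stratified score (Miettinen-Nurminen) method in place of the normal approximation. For consistency, use the same interval method for the primary endpoint and record that change in Appendix 2.

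The cost is a few sentences and a standard software option, with no new data or design change. The score interval is slightly wider and somewhat conservative in near-empty cells. The main test remains asymptotic there, with Fisher's result shown beside it.
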